#### Secondary

Acute toxicity: assessed at the week 4 visit using RTOG Acute Radiation Morbidity Scoring Criteria

Late toxicity: assessed using RTOG/EORTC Late Radiation Morbidity Scoring Criteria or, if the RTOG criteria are not applicable, using the Common Terminology Criteria for Adverse Events v3.0 (CTCAE), available online at:

http://ctep.cancer.gov/protocolDevelopment/electronic\_applications/docs/ctcaev3.pdf

 $\underline{\textit{Response}}$ : assessed at the 12 weeks from randomisation using RECIST criteria

Overall survival: time from randomisation to date of death of any cause

Health economic assessment: details of protocol treatments, other anti-cancer treatments (excluding complementary therapy), management of adverse events, hospital admission episodes, and EQ-5D questionnaire

## 5.3 Sample Size

The aim of the trial is to demonstrate that low dose radiotherapy is as effective as conventional dose radiotherapy in terms of time to tumour progression within the irradiated

field. Therefore it is designed as a non-inferiority trial with the sample size planned to reliably exclude a minimum of 10% reduction in 2-year local progression free interval within the irradiated field in the experimental arm. The following table shows the total number of patients required with 5% significance level (one-sided) and 90% power in a 4-year accrual and 1-year follow up. The 2-year local progression free interval in the control arm was reported to be about 50%. The null hypothesis of non-inferiority will be rejected if the 10% difference specified in the table is excluded in the 95% upper confidence interval limit, calculated once the study is completed. We aim to accrual a total of 650 patients over 4 years.

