## 3.12 Trial closure

The trial will be considered closed 5 years after the last patient is recruited. However, further observational follow up of all patients enrolled in the trial will continue until all randomised patients have died. This will initially be via the hospital, but in the longer term may employ national registers.

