**Table 2: Calculation of Sample Size** 

2-year PFS	Maximum of 10% reduction		N. C.	N. C. C.
in the control	in 2-year PFS in the	HR	No. of events	No. of patients
arm	experiment			
40%	30%	1.31	471	627
50%	40%	1.32	446	671
60%	50%	1.36	364	642

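### The target of 650 patients is below the 671 that Table 2 gives for the assumed 50% control rate, and with equally effective arms it yields about 401 events and about 87% power, not 446 and 90%

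*Protocol*

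**What the plan says.** Protocol section 5.3 sets a non-inferiority design for the time to progression inside the irradiated field, and the aim is to show that low dose is as effective as conventional dose. Table 2 lists the numbers "required with 5% significance level (one-sided) and 90% power in a 4-year accrual and 1-year follow up". On the control arm the text says "The 2-year local progression free interval in the control arm was reported to be about 50" per cent. The Table 2 row for that rate reads "50% 40% 1.32 446 671", that is: control rate, experimental rate at the margin, hazard ratio, events, patients. The other two rows give 471 events and 627 patients (40% v 30%, HR 1.31), and 364 events and 642 patients (60% v 50%, HR 1.36).

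The target is then "We aim to accrual a total of 650 patients over 4 years". Section 1.1 repeats 650. Section 5.1 fixes 1:1 allocation.

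On timing, section 5.3 says that the confidence limit is "calculated once the study is completed". Section 3.12 says "The trial will be considered closed 5 years after the last patient is recruited". Appendix 4 schedules visits to 5 years.

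**The concern.** Two things do not fit together.

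First, the target matches none of the three rows (627, 671, 642). It is 21 patients (3%) below the row for the rate that the text adopts, and no reason is given.

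Second, in a non-inferiority trial the stated power is the chance of excluding the margin when the arms do not differ. The number of events must then be projected with both arms at the control rate. If the experimental arm is projected at the margin instead, it progresses faster, more events are expected, and too few patients appear to be enough. The protocol does not say which event rates turned events into patients, so this has to be checked by reproducing the table.

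At stake is the power of the primary comparison at the planned data cut, and how an inconclusive result would be read.

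**Working it through.** **Inputs.** All from sections 5.1 and 5.3 and Table 2: one-sided 5% (z = 1.645), 90% power (z = 1.282), 1:1 allocation, 4 years of accrual, 1 year of follow-up, control rate 50% at 2 years, margin 40% at 2 years. Assumed because the document does not state them: exponential times, uniform accrual, no censoring by death or loss.

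**1. The plan's events.** Margin HR = ln(0.40)/ln(0.50) = 1.3219. Freedman's formula gives [(HR+1)/(HR−1)]² × (1.645+1.282)² = 446 after rounding up, exactly as stated. Schoenfeld's formula gives 440. Two-sided 5% would give 540 to 547, so the table does use one-sided 5%.

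**2. Probability of an event by the data cut.** With λ = −ln(S₂)/2, where S₂ is the 2-year rate,

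P = 1 − (e^(−λ) − e^(−5λ))/(4λ).

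This gives 0.7930 at S₂ = 30%, 0.7101 at 40%, 0.6174 at 50% and 0.5148 at 60%.

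**3. The plan's patient numbers.** Patients = stated events / P. The mixed value averages P over the control rate and the margin rate. The equal-arms value uses the control rate for both arms.

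| Control rate | Stated events | Stated patients | Mixed P | Patients, mixed | Patients, equal arms |
|---|---|---|---|---|---|
| 40% | 471 | 627 | 0.7516 | 627 | 663 |
| 50% | 446 | 671 | 0.6638 | 672 | 722 |
| 60% | 364 | 642 | 0.5661 | 643 | 707 |

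All three rows match within one patient under the mixed rate. None matches with equal arms.

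**4. Events and power at the 50% control rate.** Events = N × P. Power is Φ(√d/2 × ln HR − 1.645) (Schoenfeld) or Φ(√d × (HR−1)/(HR+1) − 1.645) (Freedman), with d events and HR = 1.3219. The range shown is Freedman to Schoenfeld.

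| Patients | Event rate | Events | Power |
|---|---|---|---|
| 671 | mixed | 445 | 90.0–90.3% |
| 650 | mixed | 431 | 89.2–89.5% |
| 671 | equal arms | 414 | 88.0–88.4% |
| 650 | equal arms | 401 | 87.1–87.5% |

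A simulation of 10,000 trials with a Cox one-sided 95% upper limit gave 87.7% power at 650 patients and 90.1% at 722, both with equal arms.

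**5. Other control rates, 650 patients, equal arms.** At 40%: 462 events and 89.8–90.1% power. At 60%: 335 events and 87.0–87.4% power.

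**6. Time at which 650 patients reach 446 events** (equal arms, 50%). With no losses this is 1.57 years after the last patient. The document gives no loss rate. If constant censoring of 2%, 5% or 10% per year is assumed, the time becomes about 1.8, 2.1 or 3.1 years. The same assumed rates would leave about 391, 376 or 354 events at the 1-year cut. At 5 years after the last patient, with no losses, about 588 events would have occurred and power would be about 96%.

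**The case against.** The case for leaving the section alone has four parts.

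- **Table 2 can be read as a grid over plausible control rates, with 650 a rounded target inside it.** 650 covers two of the three rows, and their mean is 647. On the table's own method 650 gives about 89 to 92% power across the rows. This is a fair account of how 650 may have arisen, but the protocol does not give it, and the text singles out about 50%.
- **The loss is small.** It is 2.3 to 2.9 points in total. The visible shortfall, 650 against 671, costs only about 1 point. This stands, and it limits the weight of the finding.
- **The event-rate convention is inferred.** The protocol never states it. That is true, but three rows out of three reproduce within one patient under one convention and miss by 36 to 65 patients under the other.
- **Longer follow-up would cure the problem.** Visits run to 5 years. This is correct, but section 5.3 states its power for 1 year of follow-up.

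A reader might go further and infer that the stated events, patients, follow-up and power cannot be reconciled on any reading. The document does not support that. With a 40% control rate, 650 patients and equal arms give about 90% power, and an analysis 5 years after the last patient would have about 96%.

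A reader might also infer that the protocol sets two conflicting analysis dates. That requires equating completion of the study in section 5.3 with the closure defined in section 3.12. Section 5.3 does not make that link, and its phrase may only contrast the final analysis with the interim ones. The wording is ambiguous, which is a lesser fault.

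**Conclusion.** The point holds, as something that should be fixed but does not threaten the trial. At the control rate the protocol adopts, with equally effective arms and the 4+1 year cut, 650 patients deliver about 401 events and about 87% power, against the 446 events and 90% stated. About 1 point comes from setting the target below the table's own row and about 2 points from counting events with the experimental arm at the margin.

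The figure rests on exponential times, uniform accrual, no losses and a control rate of exactly 50%. It is about 90% if the control rate is 40% and about 87% if it is 60%. Death is not an event in the endpoint defined in section 5.2, so deaths without local progression, like losses, would reduce events and power further. By how much cannot be said from the document, because it gives no rate.

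**What to change.** 1. In Table 2, recompute the patient column with both arms at the control rate: about 663, 722 and 707 patients for the stated 471, 446 and 364 events. Name the assumptions.
2. In section 5.3, keep 650 and say what it delivers: about 400 events and about 87% power at a 50% control rate with 4 years of accrual and 1 year of follow-up, assuming exponential times, uniform accrual and no losses. Give the reason for choosing 650.
3. State when the primary confidence limit is calculated, in place of the present reference to completion of the study.
4. Optionally, time the primary analysis at 446 in-field progressions. With no losses that falls about 1.6 years after the last patient, about 7 months later than the 1-year plan (0.57 × 12). With assumed losses of 2 to 10% per year it falls at about 1.8 to 3.1 years, a delay of about 9 to 25 months.

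Items 1 to 3 change only wording and a table. None of the four adds patients, and item 4 needs no new visits because follow-up is already scheduled to 5 years. Its cost is a later primary result.

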**Table 2: Calculation of Sample Size** 

2-year PFS	Maximum of 10% reduction		N. C.	N. C. C.
in the control	in 2-year PFS in the	HR	No. of events	No. of patients
arm	experiment			
40%	30%	1.31	471	627
50%	40%	1.32	446	671
60%	50%	1.36	364	642

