# 5. STATISTICAL CONSIDERATIONS

#### 5.1 Method of Randomisation

Once written informed consent has been obtained, the completed registration and randomisation forms must be faxed to CR UK & UCL Cancer Trials Centre. Eligibility will be confirmed, and then the patient will be randomised. Randomisation will be at a 1:1 ratio and will be stratified by histology (follicular lymphoma vs. marginal zone lymphoma), and whether treatment is being given with curative or palliative intent.

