#### 5.2 Outcome Measures

### **Primary**

Local progression free interval: time from randomisation to tumour progression **within the irradiated field** by clinical examination and imaging as appropriate for site of treatment and lymph nodes

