# 5.4 Analysis Plan

Analyses will be performed on an intention-to-treat basis. The standard log-rank approach will be applied for local progression-free interval and overall survival analysis. Comparisons of response and toxicity will be made by chi-squared tests or Mann-Whitney test wherever is appropriate.

No subgroup analyses are planned, although the size of node/lymphoma mass to be treated will be studied in an exploratory manner.

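### Table 2 labels the sizing rates as PFS although the endpoint is in-field progression, and its 671 patients allow for no death or loss before progression

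*Protocol*

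**What the plan says.** Protocol section 5.2 defines the primary outcome, local progression free interval, as "time from randomisation to tumour progression" within the irradiated field. Death is not part of the definition; it appears separately, under overall survival.

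Section 5.3 is written for the same endpoint. The trial is to "reliably exclude a minimum of 10% reduction in 2-year local progression free interval within the irradiated field in the experimental arm". The control rate is also given in those terms: "The 2-year local progression free interval in the control arm was reported to be about 50"%. The table is introduced as the "total number of patients required with 5% significance level (one-sided) and 90% power in a 4-year accrual and 1-year follow up".

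Table 2 then heads its control and margin columns as 2-year PFS ("in 2-year PFS in the" experimental arm). The row for a 50% control rate reads "50% 40% 1.32 446 671": control rate, margin rate, HR, events, patients. PFS is not in the Abbreviations and Glossary and appears nowhere else in the protocol. The non-inferiority criterion in section 5.3 refers back to the 10-point difference in this table. The recruitment target is 650 over 4 years.

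Section 5.4 fixes the analysis: "The standard log-rank approach will be applied for local progression-free interval and overall survival analysis".

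Neither section 5.3 nor Table 2 states an allowance for deaths or losses.

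**The concern.** There are two linked problems.

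First, the label. PFS as usually understood counts death, and progression at any site. The primary endpoint counts neither death nor progression outside the field. The table that fixes the margin therefore names a different quantity from the endpoint definition. It also leaves open whether the 50% taken from the earlier dose trial is an in-field rate.

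Second, the missing allowance. A patient who dies or is lost before in-field progression contributes no primary event. Such patients should be expected: section 2.1 admits patients treated for palliation, section 2.2 excludes only a predicted prognosis below three months, and section 3.11 plans for loss to follow-up. If 671 patients were derived as though none of this happens, fewer than 446 events will have occurred one year after accrual ends, and power at that date is below the stated 90%.

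**Working it through.** **Inputs.** From sections 5.1 and 5.3 and Table 2: one-sided 5% level, 90% power, 1:1 allocation, 2-year rates 50% and 40%, accrual A = 4 years, follow-up F = 1 year, 671 patients in the table and 650 as target. Assumed, because the protocol gives no figure: exponential times, uniform accrual, and a constant hazard d of death or loss before in-field progression of 0.02, 0.05 or 0.10 per year, equal in both arms and independent of progression.

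**Step 1: events.** The margin HR is ln(0.40)/ln(0.50) = 1.322, printed as 1.32. The Schoenfeld formula at 1.32 gives 4 × (1.645 + 1.282)² / (ln 1.32)² = 445 events. The Freedman formula at 1.322 gives 446. Conversely, 446 events give power Φ(√446/2 × ln 1.32 − 1.645) = Φ(1.287) = 0.90. So the 446 is correct for in-field progression.

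**Step 2: patients, as in Table 2.** The hazards are λ0 = ln 2 / 2 = 0.3466 (control) and λ1 = −ln 0.4 / 2 = 0.4581 (margin). The probability of an observed in-field event is

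P(λ, d) = λ/(λ+d) × [1 − (e^(−(λ+d)F) − e^(−(λ+d)(A+F))) / ((λ+d)A)].

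With d = 0, P is 0.6174 and 0.7101, mean 0.6638. Then 446/0.6638 = 672, against 671 stated. The other rows reproduce in the same way: 471/0.7516 = 627 (stated 627) and 364/0.5661 = 643 (stated 642). The patient column therefore contains no allowance for death or loss.

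**Step 3: add deaths and losses.** Everything else is kept, including the table's averaging of the two arms' event probabilities. Events are N × mean P, and power is Φ(√events/2 × ln 1.32 − 1.645).

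| d per year | mean P | events, 671 | power | events, 650 | power |
|---|---|---|---|---|---|
| 0 | 0.6638 | 445 | 90% | 431 | 89% |
| 0.02 | 0.6476 | 435 | 89% | 421 | 89% |
| 0.05 | 0.6245 | 419 | 88% | 406 | 88% |
| 0.10 | 0.5888 | 395 | 87% | 383 | 86% |

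The first row shows that part of the shortfall at 650 arises only because 650 is below 671. Reading the rates as yearly probabilities instead of hazards changes the 671-patient counts by at most about two events (434, 418 and 393).

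**Step 4: longer follow-up, 650 patients.** The same formula with larger F gives:

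| F after accrual | d = 0.02 | d = 0.05 | d = 0.10 |
|---|---|---|---|
| 2 years | 488 | 467 | 436 |
| 2.5 years | 512 | 489 | 454 |
| 5 years | 580 | 548 | 500 |

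About 2 years is enough to pass 446 at 2% and 5% per year, and about 2.5 years at 10%.

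**The case against.** The best defence is that nothing beyond a heading is wrong. Section 5.3 states the aim, the margin and the 50% rate as local progression free interval, so PFS in Table 2 is most simply a mislabel. The 1-year follow-up is a sizing horizon, and the protocol does not fix it as the analysis date. Section 5.3 has the confidence limit calculated when the study is complete, and section 3.12 closes the trial 5 years after the last patient is recruited. By then 650 patients give more than 446 events at every assumed rate. This holds even if both arms follow the control hazard (563, 529 and 479 events).

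Most of this stands. It makes the loss of power modest and recoverable. It does not rescue the statement in section 5.3 that the tabulated numbers give 90% power with 1-year follow-up, and it does not remove the conflict between the table heading and section 5.2.

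A reader might infer two stronger things. One is that the 446 events and 90% power do not belong to the endpoint analysed. They do: required events depend on level, power and HR, and 446 in-field progressions give 90% power. The other is that deaths might be counted as primary events, which would pull the HR towards 1 and make non-inferiority too easy to declare. No part of the protocol tells the analyst to do so. Sections 5.2 and 5.4 name the in-field endpoint, and the disease progression form in Appendix 4 records first progression within the irradiated field. A table heading alone does not support that reading.

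**Conclusion.** The point holds in a limited form. Table 2's label contradicts the endpoint in sections 5.2 and 5.3 and needs correcting, because the decision rule relies on that table. The event count is sound. The patient count assumes no death or loss before in-field progression, so the 90% power claimed at 1-year follow-up is overstated.

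With 671 patients the loss is about 1 to 3 percentage points, for assumed rates of 2% to 10% per year. With the 650 target, power is about 89% to 86%. These figures rest on exponential times, equal and independent death rates, and the 50% being an in-field rate, as section 5.3 says. If the cited 50% does count deaths or distant progression, the in-field event rate is lower and power falls further. The protocol alone cannot settle that.

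**What to change.** 1. Relabel the Table 2 columns as 2-year local progression free rate, matching section 5.2.
2. Confirm from the source of the 50% that it is an in-field rate counting neither death nor distant progression. Recompute the table if it is not.
3. Either restate expected events and power at 1-year follow-up with an explicit rate of death and loss, for 650 patients as well as for the tabulated number, or tie the primary analysis to 446 in-field progressions.

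The cost is a text edit and one re-run of the sample-size calculation. The stated power becomes slightly lower, or the analysis comes somewhat later (about 2 to 2.5 years after accrual ends instead of 1, with 650 patients at the assumed rates). No extra patients are needed if the analysis is event-driven.

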# 5.4 Analysis Plan

Analyses will be performed on an intention-to-treat basis. The standard log-rank approach will be applied for local progression-free interval and overall survival analysis. Comparisons of response and toxicity will be made by chi-squared tests or Mann-Whitney test wherever is appropriate.

No subgroup analyses are planned, although the size of node/lymphoma mass to be treated will be studied in an exploratory manner.

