# 4.1 Withdrawal from trial therapy

Patients may be withdrawn from treatment for any of the following reasons: -

- Disease progression within the irradiated field whilst on therapy/treatment
- ii. Patient withdraws consent
- iii. Unacceptable toxicity
- iv. Intercurrent illness, which prevents further treatment
- v. Any change in the patient's condition which justifies the discontinuation of treatment in the clinicians opinion

Data regarding a patient withdrawal prior to or during radiotherapy should be recorded on the Withdrawal From Treatment CRF. This form is only applicable for patients who either do not start, or fail to complete their randomised radiotherapy treatment. Patients who withdraw from the trial for other reasons have previously consented to follow up in the trial. If a patient wishes to withdraw from trial treatment, sites should nevertheless explain the importance of remaining on trial follow up, or failing this of allowing routine follow up data to be used for trial purposes.

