# 7.2 Ethical approval

The protocol will be approved by the Cambridgeshire 4 Research Ethics Committee (formerly the Eastern MREC), and in addition Site Specific Approval must be obtained at each institution before patients are entered at that site.

The patient's consent to participate in the trial should be obtained after a full explanation has been given of the treatment options, including the conventional and generally accepted methods of treatment. Patients should be given sufficient time after being given the trial patient

information sheet to consider and discuss participation in the trial with friends and family. A contact number should be given to the patient should they wish to discuss any aspect of the trial. Following this, the randomising investigator should determine that the patient is fully informed of the trial and their participation, in accordance with ICH GCP guidelines. Patients should always be asked to sign a consent form. One copy should be given to the patient, one copy should be kept with patient's hospital notes and one copy should be kept in the local investigator's file.

The right of the patient to refuse to participate in the trial without giving reasons must be respected. After the patient has entered the trial, the investigator must remain free to give alternative treatment to that specified in the protocol, at any stage, if he/she feels it to be in the best interest of the patient. However, the reason for doing so should be recorded and the patient will remain within the trial for the purpose of follow up and data analysis according to the treatment option to which he/she has been allocated. Similarly, the patient must remain free to withdraw at any time from the protocol treatment without giving reasons and without prejudicing his/her further treatment.

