# **APPENDIX 4: FOLLOW UP SCHEDULE**

Table 3 shows the visit schedule for the FoRT trial

Table 3: FoRT trial visit schedule

Visit number	Timepoint
1	Baseline
2	4 weeks post randomisation
3	12 weeks post randomisation – response assessment
4	6 months post randomisation
5	1 year post randomisation
6	18 months post randomisation
7	2 years post randomisation
8	3 years post randomisation
9	4 years post randomisation
10	5 years post randomisation

Once the five years of scheduled follow up are completed, patients will be followed up for survival annually until death.

The forms due at each visit are summarised in table 4 below.

Table 4: Forms due at each clinic visit

Form	Details	Compulsory / as required
Registration form	4 pages to be completed at visit 1 and faxed to UCL CTC	Compulsory
Randomisation form	1 page to be completed at visit 1 and faxed to UCL CTC	Compulsory
4-week follow up form	1 page to be posted to UCL CTC within 8 weeks of visit 2	Compulsory
Acute toxicity form	1 page to be posted to UCL CTC to be completed at visit 2 as required and posted to the UCL CTC within 8 weeks of visit 2 along with 4-week follow up form	Only required if patient experienced acute toxicity from radiotherapy
12-week follow up form	4 pages to be posted to UCL CTC within 8 weeks of visit 3	Compulsory
Follow up form	1 page to be completed at visits 4 – 10 and posted to UCL CTC within 8 weeks of visit	Compulsory up to the point of local progression
Late toxicity form	1 page to be completed at visit 3 – 10 as required and posted to UCL CTC within 8 weeks of the relevant visit along with the follow up form	Only required if patient experienced late toxicity from radiotherapy
Disease progression form	1 page to be completed at first progression within the irradiated field	Only required at local progression
Disease progression follow up form	1 page to be completed at all scheduled visits after local progression instead of the follow up form	Compulsory after local progression
Anti-cancer treatment form	1 page to be completed at visits 2-10 as required and posted to UCL CTC within 8 weeks of the relevant visit along with the follow up form	Only required if patient received cancer treatment other than their trial radiotherapy
Hospital admission form	1 page to be completed at visits 2-10 as required and posted to UCL CTC within 8 weeks of the relevant visit along with the follow up form	Only required if patient is admitted to hospital

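### Section 5.4 puts the toxicity comparison on the allocated arm, which dilutes it if patients are not irradiated or receive the other schedule; a treated-patient table by schedule started would be a cheap improvement

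*Protocol*

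**What the plan says.** Section 5.4 (Analysis Plan) opens with the rule "Analyses will be performed on an intention-to-treat basis". The same paragraph assigns the log-rank approach to local progression free interval and overall survival, and then states: "Comparisons of response and toxicity will be made by chi-squared tests or Mann-Whitney test wherever is appropriate". It exempts no outcome, and no section of the protocol defines a separate population for safety.

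Section 7.2 (Ethical approval) gives the same rule for departures from treatment. It says that "the investigator must remain free to give alternative treatment to that specified in the protocol, at any stage", and that such a patient stays in the trial for "follow up and data analysis according to the treatment option to which he/she has been allocated".

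Section 4.1 provides a withdrawal-from-treatment form and says of it: "This form is only applicable for patients who either do not start, or fail to complete their randomised radiotherapy treatment". Patients with no radiotherapy or incomplete radiotherapy are thus expected.

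Section 5.2 lists acute and late toxicity as secondary outcomes. Acute toxicity is "assessed at the week 4 visit using RTOG Acute Radiation Morbidity Scoring Criteria". In Appendix 4, Table 4, the acute toxicity form is "Only required if patient experienced acute toxicity from radiotherapy", and the late toxicity form carries the matching condition.

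**The concern.** Intention-to-treat fits an outcome that every randomised patient can have. The toxicity recorded here is radiation morbidity: the scoring guidelines in Appendix 2 concern effects of radiation therapy and ask the evaluator to separate them from effects of disease. A patient who never starts radiotherapy cannot have this outcome and returns no toxicity form, yet under Section 5.4 stays in the denominator as an apparent success. A patient treated on the other schedule contributes that schedule's toxicity to the allocated arm.

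The trial is open-label (Section 1.2), so departures from allocation are possible. Toxicity by schedule is what a reader would weigh against any loss of local control with 4Gy. If departures occur in similar shares in both arms, the rule pulls that contrast toward no difference, and neither arm's rate describes its own schedule. The point concerns the toxicity comparison only. It does not touch the non-inferiority analysis or the sample size in Table 2.

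**Working it through.** The plan states no toxicity rate and no share of patients off allocation, so there is no figure of its own to reproduce. The check is a mixture calculation.

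**Inputs from the protocol.** Analysis is by allocated arm (Sections 5.4 and 7.2). Randomisation is 1:1 (Section 5.1). Toxicity forms are completed only for toxicity attributed to radiotherapy (Appendix 4, Table 4), from which it follows that an untreated patient contributes zero.

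**Assumed inputs, not in the protocol.** In each arm a share x is treated on the other schedule and a share u receives no radiotherapy. The true toxicity rates by schedule are t24 and t4. For illustration, t24 = 25% and t4 = 5%, a difference of 20 points.

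**Formulas.**

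- 24Gy arm by allocation: R24 = (1 − x − u)·t24 + x·t4
- 4Gy arm by allocation: R4 = (1 − x − u)·t4 + x·t24
- Difference: R24 − R4 = (1 − 2x − u)·(t24 − t4)

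The factor 1 − 2x − u does not depend on the toxicity rates.

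**Results with equal deviations in both arms.**

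| x | u | factor | 24Gy arm | 4Gy arm | difference (points) |
|---|---|---|---|---|---|
| 0 | 0 | 1.00 | 25.0% | 5.0% | 20.0 |
| 1% | 1% | 0.97 | 24.55% | 5.15% | 19.4 |
| 2% | 3% | 0.93 | 23.85% | 5.25% | 18.6 |
| 5% | 2% | 0.88 | 23.5% | 5.9% | 17.6 |
| 5% | 5% | 0.85 | 22.75% | 5.75% | 17.0 |
| 10% | 5% | 0.75 | 21.75% | 6.75% | 15.0 |

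For the row x = 5%, u = 2%: 0.93 × 25 + 0.05 × 5 = 23.5 and 0.93 × 5 + 0.05 × 25 = 5.9.

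**Unequal deviations.** If 10% of the 4Gy arm receive 24Gy, none cross the other way and 2% of each arm are untreated, the 4Gy arm reads 0.88 × 5 + 0.10 × 25 = 6.9%. The 24Gy arm reads 0.98 × 25 = 24.5%. Crossing in one arm only still shrinks the difference. Non-treatment confined to the 4Gy arm works the other way: it lowers that arm's rate by u·t4, which is 0.02 × 5 = 0.1 point at u = 2%, and so slightly widens the difference. Shrinkage is therefore assured for equal deviations, not for every pattern.

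**Which grouping to use instead.** Each fraction is 2Gy (Section 1.1), and Section 4.1 lists unacceptable toxicity as a reason to stop. A patient on the 24Gy schedule who stops for toxicity after two or three fractions has received 4Gy or 6Gy. Grouping by cumulative dose delivered would place this patient in or near the 4Gy group and move a toxicity event away from the schedule that caused it. Grouping by the schedule started avoids this.

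**The case against.** The strongest reply is that by-allocation toxicity answers a legitimate question, namely what follows from choosing one schedule over the other, and that this comparison keeps the protection of randomisation. That stands. A reader might infer that the toxicity rates will be wrong; the documents do not support that. The two analyses part only if patients go untreated or receive the other schedule, and no rate is given for either. Courses are short (2 consecutive days or 16 days), so departures may be few.

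A reader might also infer that the protocol expects crossover between the two trial doses. It does not say so. Section 7.2 is a general clause on alternative treatment and does not name the other schedule, and Section 4.1 covers not starting and not completing. Non-treatment is foreseen directly, a switch of schedule only by implication.

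Nor does the protocol present lower toxicity as the main benefit of 4Gy. Its rationale in Sections 1.5 and 1.6 is efficiency and the use of linear accelerators, and Appendix 2 treats only grades 1 and 2 as expected in this trial. Shrinkage would also understate any toxicity advantage of 4Gy, so the rule is unlikely to flatter the experimental arm.

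Finally, safety populations are often left to the statistical analysis plan, which is not shown, and nothing in the protocol forbids an additional table. But this is not a gap. Section 5.4 covers toxicity with an unqualified rule and Section 7.2 repeats it, so a plan that replaced it with a treated-patient analysis would depart from the protocol.

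**Conclusion.** The point holds in a limited form. The protocol sets a by-allocation rule for an outcome that only irradiated patients can have. If equal shares of both arms deviate, the toxicity difference is multiplied by 1 − 2x − u: a 3% loss at x = u = 1%, 12% at x = 5%, u = 2%, and 25% at x = 10%, u = 5%. The factor rests on assumed shares and on untreated patients being counted as free of toxicity; the rates in points rest further on the assumed 25% and 5%. At low deviation the effect is negligible. The data needed for a better table are already collected, and the rule distorts only a secondary comparison. This is a cheap improvement of minor to moderate importance, not an error that endangers the trial's conclusions.

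**What to change.** In Section 5.4, limit the intention-to-treat sentence to local progression free interval, overall survival and response. Add that acute and late toxicity are analysed in patients who received at least one fraction, grouped by the radiotherapy schedule they started and not by cumulative dose delivered, so that a patient who stops the 24Gy schedule early for toxicity stays in the 24Gy group. Report the by-allocation toxicity table alongside. Align Section 7.2, where "data analysis according to the treatment option to which he/she has been allocated" is stated without exception, so that the two sections agree.

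The cost is a sentence or two and one extra table. The withdrawal-from-treatment form identifies non-starters, the anti-cancer treatment form records other treatment, and Section 5.2 already lists details of protocol treatments among the data to be collected. The sample size is unaffected. The downside is that the treated groups are no longer strictly as randomised, which is why the by-allocation table should be kept. Section 3.6 permits further anti-cancer therapy, so later treatment can still affect late toxicity in either table.
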